16.1.6.3. Patient-reported outcome

Missing results will not be imputed for patient reported outcome and will be indicated as “Missing” in tables. If any questionnaire response is missing then health index score (HIS) will also be set to be missing for that patient at specific visit.

16.1.7. ANALYSIS OF SECONDARY EFFICACY VARIABLES

16.1.7.1. Analysis of DRC-adjudicated and Investigator-assessed overall response

Analyses of these secondary efficacy variables will be similar to the analysis of the primary efficacy variable.

Document: \\weedc-vnasc01\BIOSdata\F2G\F901318\ [Redacted]
Author: [Redacted] Version Number: 3.0
Version Date: 06Apr2023
Template No.: CS_TP_BS016 Revision 6 Reference: CS_WI_BS005
Effective Date: 02Dec2019

F2G Ltd.
PROTOCOL F901318/0032

16.1.7.2. Analysis of DRC-adjudicated and Investigator-assessed clinical response

Based on the DRC-adjudicated and Investigator-assessed clinical response categorized as success or failure (as defined above in Section 16.2.1.3), a response rate will be calculated for the proportion of successes. In addition, a 95% exact Clopper-Pearson CI for the single binomial proportion (Clopper & Pearson, 1934) will be calculated.

All DRC-adjudicated clinical response data will be summarised descriptively and listed. Investigator-assessed clinical response data will be summarised descriptively and listed including extended phase data.

Clinical signs and symptoms data, as collected on the Screening Assessment of Clinical Signs and Symptoms and Assessment of Clinical Signs and Symptoms eCRF pages, will be summarised descriptively and listed.

16.1.7.3. Analysis of DRC-adjudicated and Investigator-assessed radiological response

DRC-adjudicated and Investigator-assessed radiological response will be summarised descriptively and listed.

Radiological assessment data, as captured on the Radiologic Assessment eCRF page, and central radiology data, as obtained from the external vendor Bioclinica, will be summarised descriptively and listed.

16.1.7.4. Analysis of DRC-adjudicated and Investigator-assessed mycological response

Based on the DRC-adjudicated and Investigator-assessed mycological response categorized as success or failure (as defined above in Section 16.2.1.5), a response rate will be calculated for the proportion of successes. In addition, a 95% exact Clopper-Pearson CI for the single binomial proportion (Clopper & Pearson, 1934) will be calculated.

Serum galactomannan (GM antigen) will be assessed for all patients with proven or probable IA. Summary table for serum GM will be presented by visits and baseline DRC adjudicated disease categories. Plot of Serum GM (mean +/- SD) by visits and baseline DRC adjudicated disease categories will be presented. Spaghetti plot for serum GM over visits will be presented.

The following data will also be listed:

- Bronchoscopic assessment data, as captured on the Bronchoscopic Assessments eCRF page.
- Other microbiological assessment data, as captured on the Other Microbiological Assessments eCRF page.
- Other mycological (fungal) assessment data, as captured on the Other Mycological (Fungal) Assessments eCRF page.

Document: \\weedc-vnasc01\BIOSdata\F2G\F901318\ [Redacted]
Author: [Redacted] Version Number: 3.0
Version Date: 06Apr2023
Template No.: CS_TP_BS016 Revision 6 Reference: CS_WI_BS005
Effective Date: 02Dec2019

- Histology/cytology*, as captured on the Histology/Cytology eCRF page.
- Fungal culture data*, as captured on the Fungal Culture eCRF page.
- GM antigen data*, as captured on the GM Antigen – Central, GM Antigen – Central Repeat, and GM Antigen – Local eCRF pages.
- Polymerase Chain Reaction data*, as captured on the PCR – Polymerase Chain Reaction eCRF page.
- Susceptibility Testing data, as captured on the Susceptibility Testing eCRF page.
- Cocci serology local and central data, as captured on the Cocci Serology eCRF page.

*Samples may be shipped to the central general/cocci mycology laboratories, and all data from the central mycology laboratories (general and cocci) will also be listed.

16.1.7.5. Analysis of all-cause mortality rate

Survival status data are collected at Day 42 visit, at main study phase EOT visit, at Day 84 visit, and at the 4-week follow-up visit. Where survival status was not collected at the visit, additional methods of ascertaining survival status will be used including safety reviews conducted by the sponsor and last known contact date using other information collected in the eCRF.

The all-cause mortality rates at Day 42, at main study phase EOT, at Day 84, and at 4-week follow-up will be calculated using the expression described in section 16.2.1.6 for mortality rate at visit X.

In addition, a 95% exact Clopper-Pearson CI for a single binomial proportion (Clopper & Pearson, 1934) will be calculated.

A survival analysis will be performed using the survival status data stratified by baseline DRC-adjudicated disease category. Overall survival is defined as the time from the date of first dose of study drug until death due to any cause in general. Patients not known to have died at the time of data cut-off will be censored at the last date known to be alive on the main study. Overall survival will be presented graphically using the Kaplan-Meier plots. The Kaplan-Meier plots will be truncated when the number of patients at risk is <5, as beyond this point interpretation is problematic due to the large degree of uncertainty in any estimates provided.. The estimated overall survival rates at Day 42, Day 84 and Day 112 will be estimated via the Kaplan-Meier method. The corresponding 95% CI (using the Greenwood formula method of Kalbfleisch and Prentice, 1980) for each estimated overall survival rate will be presented. Also, median overall survival and the corresponding 95% CI (using the method of Brookmeyer and Crowley, 1982 with the log-log transformation) will be summarized. The cumulative number and % of subjects who

Document: \\weedc-vnasc01\BIOSdata\F2G\F901318\ [Redacted]
Author: [Redacted] Version Number: 3.0
Version Date: 06Apr2023
Template No.: CS_TP_BS016 Revision 6 Reference: CS_WI_BS005
Effective Date: 02Dec2019

died before or during each of the landmark time points Day 42, Day 84 and Day 100 will be presented.

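### The overall survival analysis uses different windows for deaths and for censoring: read literally, an extended-treatment patient stays at risk after about Day 90 only by later dying, which biases the median and the late curve downward

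*SAP*

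**What the plan says.** SAP 16.1.7.5 sets up a Kaplan-Meier analysis stratified by baseline disease category. The event has no phase or time limit: "Overall survival is defined as the time from the date of first dose of study drug until death due to any cause in general". Two parts of one sentence then fix the censoring. It applies to "Patients not known to have died at the time of data cut-off", and these patients "will be censored at the last date known to be alive on the main study".

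The outputs are landmark rates ("The estimated overall survival rates at Day 42, Day 84 and Day 112 will be estimated via the Kaplan-Meier method"), a median ("Also, median overall survival and the corresponding 95% CI") and plots. The only safeguard for thin risk sets concerns the plots: "The Kaplan-Meier plots will be truncated when the number of patients at risk is <5".

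For a patient who continues into ET, the end-of-treatment and end-of-study visits of the main phase are one visit at about Day 84 to 90 (Protocol 4.1; SAP 3.1), and there is no main-phase 4-week follow-up visit (Protocol 8.8.2, note). Survival status is still recorded at each ET visit and at the post-ET follow-up (Protocol 6.3.2).

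**The concern.** Status is judged at one date and survivors are censored at another, earlier one. An ET patient alive at cut-off is censored at about Day 90. An ET patient who died on, say, Day 200 is an event at Day 200 and counts as at risk from Day 90 to Day 200. Being in the risk set after Day 90 then depends on the outcome, whatever the true mortality.

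The median, its confidence interval and the curve beyond main-study follow-up are at stake, and the bias runs against the drug. Because the analysis is stratified, a small disease category is most exposed: if the last patient at risk there is one late ET death, the curve ends at 0% on that day. A reader would take the median as survival of all treated patients.

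**Working it through.** The plan states no figure that depends on this rule, so there is nothing to reproduce. The check applies the product-limit formula, S(t) = product of (1 − deaths/at risk), to three rules: the literal text; deaths and censoring both stopped at main-study end; deaths and censoring both run to cut-off.

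**Inputs from the documents.** About 200 patients (SAP 3.1). ET patients leave the main study at about Day 90. The last scheduled non-ET follow-up is 90 days of treatment + 28 days + a 7-day window = Day 125 (Protocol 5.1 and Table 1). The ET share of 25% is an assumption prompted by the rationale for Amendment 04 (Protocol Appendix 4).

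**Assumed, not in the documents.** 40 deaths before Day 84. Of 110 non-ET survivors, 55 end at Day 84 and 55 at Day 115, with no deaths between. Of 50 ET patients, 8 die, on Days 95, 105, 130, 160, 200, 260, 300 and 365; the other 42 are alive at cut-off (Day 400).

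**Literal rule.**
- Day 84: 160/200 = 80.0%.
- After Day 90 the risk set is 55 non-ET + 8 future ET deaths = 63. Day 112: 0.80 × 61/63 = 77.5%.
- After Day 115 only 6 remain, all future deaths. Day 180: 0.775 × 4/6 = 51.6%. Day 200: 0.775 × 3/6 = 38.7%, so the median is Day 200. Day 365: 0%.

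**Both run to cut-off.**
- After Day 90 the risk set is 55 + 50 = 105. Day 112: 0.80 × 103/105 = 78.5%.
- After Day 115 it is 42 + 6 = 48. Day 180: 0.785 × 46/48 = 75.2%. Day 365: 0.785 × 42/48 = 68.7%.

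| Rule | Day 84 | Day 112 | Day 180 | Day 365 | Median |
|---|---|---|---|---|---|
| Literal | 80.0% | 77.5% | 51.6% | 0.0% | Day 200 |
| Both stop at main-study end | 80.0% | 80.0% | nobody at risk | nobody at risk | not reached |
| Both run to cut-off | 80.0% | 78.5% | 75.2% | 68.7% | not reached |

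Under the literal rule 4 patients are at risk after the Day 160 death, so the plot would be cut there. The Day 200 median would still appear in the table.

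**Simulation (300 runs per scenario, all rates assumed).** Day 84 mortality was 20% (30% also tried), one-year mortality after Day 90 was 10%, 20% or 30%, and the ET share was 25% (40% also tried). Half of non-ET patients finished treatment at Day 84 to 90 (20% also tried). ET follow-up ran to at most 730 days with 100 patients and 1500 with 200. Non-ET deaths counted only to main-study end.
- Day 84: no difference from true survival.
- Day 112: literal survival 0.1 to 0.7 points below true.
- Day 180: 4.9 to 7.0 points below with 200 patients; 14.3 to 15.5 points below with 100.
- A finite median appeared in 89% to 100% of literal-rule runs, and in none when both windows stopped at main-study end.
- With 200 patients, 25% ET and 20% one-year mortality, the median was about Day 326 under the literal rule, against about Day 846 when both ran to cut-off.

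**The case against.** The strongest reply is that only main-phase deaths were ever meant, and it has real support.
- The section lists its own data source: "Survival status data are collected at Day 42 visit, at main study phase EOT visit, at Day 84 visit", plus the 4-week follow-up. All are main-phase visits.
- Protocol 6.3.2 sends ET survival to the report addendum, and Protocol 8.0 keeps ET data out of the analyses for the study report.
- Protocol 8.8.2 censors visit by visit.
- SAP 3.1 limits follow-up in the Final CSR to the main-phase end-of-study visit.
- Where the SAP wants ET data in an efficacy analysis, it says so (16.1.7.2 and 16.1.7.6). Section 16.1.7.5 does not.

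This stands as evidence of intention, so a reader should not infer that the SAP plainly directs ET deaths to be counted. It does not close the gap. No sentence in 16.1.7.5 limits deaths to the main phase, the section judges status at cut-off, and it draws on sponsor safety reviews and last-contact dates where status was not collected at a visit. SAP 4.3 points both ways: it ends the Initial CSR data at the main-study end-of-study visit, yet it includes available ET data and has ET efficacy endpoints summarised.

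A reader might also infer that Day 112 mortality is overstated by several points. That can be produced: assume 3 deaths among 55 non-ET and 3 among 50 ET patients by Day 112 (about a 6% 28-day risk) and no ET deaths afterwards. Literal mortality is then 1 − 0.8 × 52/58 = 28.3%, against 1 − 0.8 × 99/105 = 24.6% with ET follow-up used. But this needs ET mortality to stop at Day 112. If the same 6% risk continues for a year, about 26 of the 47 remaining ET patients die and the literal figure is 1 − 0.8 × 78/84 = 25.7%, a gap of about 1 point. The documents give no late mortality rate that would support the larger shift.

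**Conclusion.** The event and censoring windows do not match. Followed exactly, the text biases late survival downward. That follows from the rule and needs only some ET deaths known by cut-off; the sizes rest on assumed mortality, ET share and follow-up.

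The robust consequence is the tabulated median, its interval and the curve after about Day 112. Day 42 and Day 84 estimates, crude and Kaplan-Meier, are not affected. Day 112 is affected little: about 0 to 1 point in most scenarios.

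On the main-phase reading there is no such bias. What remains is that Day 112 rests on non-ET patients only, which the section does not state.

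Mortality is a secondary, descriptive endpoint with no decision rule attached. The correction should still be made, because two competent programmers could produce different medians from this text.

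**What to change.** Use one window for events and censoring in SAP 16.1.7.5.

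**First choice, consistent with the protocol.** Count only deaths up to each patient's main-study end. Censor everyone else, including ET patients who die later, at the last main-study date known alive. State that estimates after about Day 90, including Day 112, rest on non-ET patients only, and show the number at risk.

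**Alternative, or for the ET addendum.** Count deaths in any phase and censor at the last date known alive in any phase. Record this in SAP 3.3 as a change from the protocol. State that estimates after about Day 125 rest on ET patients, a group selected by completing 84 to 90 days of treatment and by the investigator's view of likely benefit (Protocol 4.3.1.1).

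Either costs a few sentences and a little programming on data already collected. The first choice uses less late follow-up; the alternative moves some ET survival data from the addendum into the main report.

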16.1.7.6. Analysis of Patient-reported outcome

Both EQ-5D-5L qualitative and quantitative items will be summarised descriptively and listed for main phase and extended phase data.

In addition, the qualitative items will be presented as shift from baseline to the scheduled visits, and also as shift from baseline to derived EOT. Qualitative items will also be presented by means of a stacked bar chart.

Summary statistics will be presented for the EQ-5D-5L index score at each visit, as well as change from baseline.

17. PHARMACOKINETIC ANALYSIS

[figure not shown]
The PK parameter calculations will be the responsibility of the clinical pharmacokineticist at IQVIA, Overland Park, Kansas, United States. The concentration summaries, PK parameter summaries, data listings, and associated graphic presentation will be the responsibility of the study biostatistician at IQVIA, Bloemfontein, South Africa.

Scheduled intensive PK day plasma concentrations and PK parameters for olorofim (central bioanalytical lab) will be summarized using descriptive statistics, including n, mean, SD, coefficient of variation (CV%), median, minimum, and maximum. geometric mean, and CV% for geometric mean (GeoCV%). For time of maximum concentration (Tmax), only n, median, minimum, and maximum will be provided. If the number of non-missing observations at a time point is fewer than 3, the data at the time point will not be summarized. Scheduled intensive PK day plasma concentrations and PK parameters will be summarised by dosing methodology (adjusted (all), adjusted (BID), adjusted (TID) or fixed dosing) using descriptive statistics, including n, mean, median, 95% CI, minimum and maximum. Intensive PK day PK parameters will also be summarised by concomitant medication (CYP3A4 inhibitors and inducers) demographics (age, sex, race) and underlying condition (immune status, baseline creatinine clearance, GvHD) using descriptive statistics, including n, mean, median, 95% CI, minimum, and maximum.

In general, scheduled trough data (central bioanalytical lab and regional hub) will be summarised by dosing methodology (adjusted or fixed dosing) and regimen (BID or TID) using descriptive statistics, including including , mean, SD, coefficient of variation (CV%), median, minimum, and maximum, geometric mean, and CV% for geometric mean (GeoCV%). Trough parameters will be summarised by dosing methodology (adjusted (all), adjusted (BID), adjusted (TID) or fixed dosing), concomitant medication (CYP3A4 inhibitors and inducers), demographics (age, sex, race) and underlying condition (immune status, baseline creatinine clearance, GvHD) using descriptive statistics, including n, mean, median, 95% CI, minimum, and maximum.

Document: \\weedc-vnasc01\BIOSdata\F2G\F901318 [REDACTED]
Author: [REDACTED] Version Number: 3.0
Version Date: 06Apr2023
Template No.: CS_TP_BS016 Revision 6 Reference: CS_WI_BS005
Effective Date: 02Dec2019

F2G Ltd.
PROTOCOL F901318/0032

Concentration data will be reported and analyzed with the same precision as the source regardless of how many significant figures or decimals the data carry. Concentration ratios will be reported to the same precision as source, with no more than three decimal places. Pharmacokinetic parameters and concentration ratios will be rounded for reporting purposes in the by-subject listings, but the unrounded values will be used for the calculation of the summary statistics and in the inferential analyses. For most derived PK parameters, 3 significant digits will be used as the standard rounding procedure for data reporting, with the following exceptions:

- Pharmacokinetic parameters directly derived from source data (C_{max} , C_{before} , $Trough_{avg}$, etc.) will be reported and analyzed with the same precision as the source data.
- Pharmacokinetic parameters derived from actual elapsed sample collection times (e.g., T_{max}) will be reported to 2 decimal places.

Reporting of mean, SD, minimum, median, maximum, and geometric mean will follow the same precision of source concentrations or the rounding convention of the individual PK values. The CV% and GeoCV% will always be reported to 1 decimal place.

17.1. PLASMA CONCENTRATION DATA

Samples for trough PK concentration determination are split into two aliquots, with one aliquot shipping to the regional hub for rapid analysis and one aliquot shipping to the central laboratory. Both laboratory results will be listed, and scheduled trough plasma concentration data will be summarised from both central and regional laboratories. Samples for intensive PK day concentration determinations will be sent to the central laboratory only and these data will be used to summarise intensive PK day plasma concentrations and parameter determination/tabulation.

A listing of PK blood sample collection times as well as derived sampling time deviations and concentrations (olorofim from both central and regional labs [redacted] from central lab) will be provided. This listing will include all samples, including unscheduled samples.

The ratio of plasma [redacted] plasma olorofim will be determined at every intensive sampling time, as appropriate, and [redacted]. If one result is below the limit of quantitation (BLQ), then BLQ will be treated as $1/2 \times$ lower limit of quantitation (LLOQ) for ratio calculations and the results will be flagged in listings as such. If both results are BLQ or one result is missing, a ratio will not be determined.

All plasma concentrations and associated ratios will be summarized by scheduled sampling time using descriptive statistics. These summaries will be presented by dosing type (Adjusted and Fixed dosing type and combined). Concentrations that are BLQ will be treated as LLOQ/2 for the computation of descriptive statistics.

Document: \\weedc-vnasc01\BIOSdata\F2G\F901318 [redacted]
Author: [redacted] Version Number: 3.0
Version Date: 06Apr2023
Template No.: CS_TP_BS016 Revision 6 Reference: CS_WI_BS005
Effective Date: 02Dec2019

Trough concentrations will be excluded from descriptive statistics and/or concomitant medication or trough parameters (described below) if the sample is collected more than 1 hour before or more than 15 minutes after its associated dose, or the time of the previous dose was not collected, or the sample was collected fewer than 5 days after the end of a temporary dose interruption. Otherwise, trough concentrations will be included in calculations and summaries regardless of sampling time deviation.

Concentrations versus time will be presented graphically as follows:

- Spaghetti plots of individual trough olorofim concentrations (scheduled and unscheduled) versus study day presented by dosing type (Adjusted and Fixed) and study phase (main and extended) based on central laboratory and regional laboratory data.
- Box/Whisker plots of trough olorofim concentrations (scheduled and unscheduled) presented by dosing type (Adjusted, Fixed and Combined) and study phase (main and extended) based on central laboratory and regional laboratory data.
- Mean (+SD) scheduled trough olorofim and [REDACTED] concentrations (central laboratory) versus study day by dosing type (Adjusted or Fixed), dosing regimen (BID and TID) and study phase (main and extended) will be presented on a linear and semi-log scale.
- By-subject olorofim trough concentrations (central lab and regional hub) (y-axis) and total daily dose (presented on a second y-axis) versus study day will be presented on a linear scale.
- Intensive PK day mean olorofim and [REDACTED] concentration-time plots by dosing type (Fixed, Adjusted (BID)) and Adjusted (TID) will be presented on a linear scale. Similar concentration-time plots [REDACTED] intensive PK mean olorofim and [REDACTED] data will be presented for the Adjusted dosing subjects dosing regimen (BID and TID).
- Box/Whisker plots of selected intensive PK day PK parameters for olorofim presented by dosing type (Adjusted, Fixed and Combined)
- Spaghetti plots of individual intensive PK day olorofim and [REDACTED] concentration-time profiles will be presented by dosing type (Fixed, Adjusted (BID) and Adjusted (TID))
By-subject intensive PK day olorofim and [REDACTED] concentration-time plots on a linear scale, with mealtimes indicated on the x-axis.

Mean and 95% confidence intervals of selected intensive PK day PK parameters for olorofim presented by concomitant medication, demographic and underlying condition sub groups

17.1.1. CONCOMITANT MEDICATIONS

Document: \\weedc-vnasc01\BIOSdata\F2G\F901318 [REDACTED]
Author: [REDACTED] Version Number: 3.0
Version Date: 06Apr2023
Template No.: CS_TP_BS016 Revision 6 Reference: CS_WI_BS005
Effective Date: 02Dec2019

F2G Ltd.
PROTOCOL F901318/0032

Selected olorofim trough parameters will be summarized by concomitant medication group (no/weak inhibitors of CYP2C9 and CYP3A4, moderate inhibitors of CYP2C9 or CYP3A4, strong inhibitors of CYP2C9 or CYP3A4, dual moderate inhibitors of CYP2C9 and CYP3A4, no/weak inducers of CYP3A4, moderate or strong inducers of CYP3A4) provided the medication has been administered to at least three subjects during the main phase of the study. Individual data will be listed for all cases where these concomitant medications are administered during the main phase of the study.

Selected olorofim PK parameters will be summarized by concomitant medication group (no/weak inhibitors of CYP2C9 and CYP3A4, moderate inhibitors of CYP2C9 or CYP3A4, strong inhibitors of CYP2C9 or CYP3A4, dual moderate inhibitors of CYP2C9 and CYP3A4, no/weak inducers of CYP3A4, moderate or strong inducers of CYP3A4) provided the medication has been administered to at least three subjects on the intensive PK day. Figures of mean and 95% confidence interval will also be presented graphically for each concomitant medication group. Individual data will be listed for all cases where these concomitant medications are administered on the intensive PK day.

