The specific combination of fluconazole (CYP3A4 and CYP2C9 inhibitor) and F901318 has been studied in man and exposure to fluconazole has been shown to increase mean AUC₀₋₁₂ and C_{max} of F901318 by 2.0 and 1.7-fold, respectively. *In vitro* and *in vivo* studies have shown that F901318 is a weak inhibitor of CYP3A4; in a clinical study treatment with F901318 resulted in an approximately 1.6-fold elevation of midazolam exposure. F901318 also shows potential for inhibition of the P-gp, BCRP, and BSEP transporters in *in vitro* studies, and whilst the potential for drug interactions is thought to be low, careful monitoring may be needed for sensitive substrates of these transporters which have narrow therapeutic windows.

Based on these findings, caution should be exercised when F901318 is dosed together with any CYP inducer (this may reduce F901318 levels) or inhibitor (this may increase F901318 levels). In addition, F901318 could increase the exposures of compounds metabolized by CYP3A4.

The Investigator is advised to consult with the MM on concomitant medications that either are metabolized by the liver or that influence hepatic metabolism. Concomitant administration of inhibitors of human DHODH (teriflunomide and leflunomide) is prohibited. Co-dosing with moderate or strong CYP3A4 or 2C9 inhibitors will require a dose reduction for F901318 and guidance on dose adjustment must be sought from the MM. It is anticipated that co-dosing with strong CYP inducers (e.g., phenytoin and rifampicin) will significantly reduce F901318 exposures and is discouraged. It is anticipated that co-dosing with immunosuppressive agents

that are sensitive CYP3A4 substrates (e.g., cyclosporine, sirolimus, or tacrolimus) will be possible, [REDACTED].

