2.0	28Feb2022	[Redacted]	
Section 7.4 Included details of deriving -azole resistance subcategory using local laboratory data, since central lab data was not available for all patients.
 
Section 12.1 Included details for imputation of partial and missing dates for medications.
 
Section 14 Added categories Duration of exposure details.
 
Section 16.1.7.5 Added details for ascertaining survival status where survival status was not collected in the eCRF.
 
Section 16.1.7.5 Added specification that Kaplan-Meier plots will be truncated when the number of patients at risk is <5. This is due to large degree of uncertainty leading to potentially misleading interpretation.
 
Section 18.4.2 Systolic Blood Pressure markedly abnormal high criteria amended to ≥ 140 mmHg based on advice from safety physicians.

Document: \\weedc-vnasc01\BIOSdata\F2G\F901318 [Redacted]
 Author: [Redacted] Version Number: 3.0
 Version Date: 06Apr2023
 Template No.: CS_TP_BS016 Revision 6 Reference: CS_WI_BS005
 Effective Date: 02Dec2019

F2G Ltd.
PROTOCOL F901318/0032

3.0	17Mar2023		
Section 7.4 added subgroup for Reason for Limited Treatment Options and updated neutropenia status derivation.
 
Section 17 added subgroups (concomitant medication, demographaics and underlying disease)
 
Sectoin 17.1 further defined acceptabel sampling widnow for trough samples
 
Section 17.1.1 revised analysis for assessing impact of concomitant medications upon olorofim exposure
 
Section 18.2.1 added derivation for Creatinine clearance
 
Section 18.3.2 added definition of retrospective and prospective ECG overreads.

-----	-----------	--	---

Document: \\weedc-vnasc01\BIOSdata\F2G\F901318

Author: Version Number: 3.0

Version Date: 06Apr2023

Template No.: CS_TP_BS016 Revision 6 Reference: CS_WI_BS005

Effective Date: 02Dec2019

F2G Ltd.
PROTOCOL F901318/0032

TABLE OF CONTENTS

1.	INTRODUCTION	12
2.	STUDY OBJECTIVES AND ESTIMANDS	12
2.1.	Primary Objective	12
2.2.	Secondary Objectives	12
2.3.	Exploratory Objectives	13
2.4.	Extended Treatment Exploratory Objectives	13
2.5.	Estimands	13
3.	STUDY DESIGN	13
3.1.	General Description	13
3.2.	Schedule of Events	17
3.3.	Changes to Analysis from Protocol	17
4.	PLANNED ANALYSES	18
4.1.	Independent Data & Safety Monitoring Board (IDSMB)	19
4.2.	DRC Analyses	19
4.3.	Analyses for initial CSR	19
4.4.	Final Analysis	20
5.	ANALYSIS SETS	20
5.1.	Process for Analysis Set Assignment	20

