2.3. EXPLORATORY OBJECTIVES

The exploratory objectives are:

- To evaluate dose adaptation and drug-drug interaction (DDI) management strategies.
- To assess potential drug interactions associated with F901318 treatment.

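### The six CYP co-medication groups in SAP 17.1.1 overlap and have no assignment rule, so descriptive comparisons of olorofim exposure between them can be confounded

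*SAP*

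**What the plan says.** SAP 17.1.1 defines the co-medication groups for both the trough parameters and the intensive-day PK parameters. After a no/weak inhibitor group, the inhibitor list continues "moderate inhibitors of CYP2C9 or CYP3A4, strong inhibitors of CYP2C9 or CYP3A4, dual moderate inhibitors of CYP2C9 and CYP3A4". The inducer list is "no/weak inducers of CYP3A4, moderate or strong inducers of CYP3A4". For the intensive-day parameters, the only condition on producing a summary is "provided the medication has been administered to at least three subjects on the intensive PK day"; the trough parameters have a matching condition for the main phase.

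The output is descriptive. "Figures of mean and 95% confidence interval will also be presented graphically for each concomitant medication group" in the intensive-day paragraph, and individual data are listed. SAP 17 plans n, mean, median, 95% CI, minimum and maximum for the co-medication subgroups. No group is called a reference, and no ratio, contrast, model or test between groups is planned.

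The purpose is nevertheless comparative. The version 3.0 entry in the SAP history describes this section as a "revised analysis for assessing impact of concomitant medications upon olorofim exposure". SAP 2.3 lists as exploratory: "To assess potential drug interactions associated with F901318 treatment". The Protocol synopsis names the effect of concomitant medication on PK profiles among the PK endpoints.

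**The concern.** A reader of the planned figure will set the moderate or strong inducer group beside the no/weak inducer group, and each inhibitor group beside the no/weak inhibitor group. The labels invite exactly that. If the unexposed group on one list contains patients exposed on the other, the difference between two means mixes two drug effects.

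Inhibitor use is to be expected in this trial. Protocol 5.9.2.1 permits fluconazole at any time and asks that patients on isavuconazole or posaconazole be switched to it. Protocol 2.1.3 says "exposure to fluconazole has been shown to increase mean" AUC over 0–12 hours and Cmax of the study drug, 2.0-fold and 1.7-fold respectively. What is at stake is whether the SAP's own tables and figures can answer the exploratory interaction question. The efficacy result is not involved.

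**Working it through.** **Step 1: place typical patients using the definitions as written.**

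| Patient takes | Inhibitor list | Inducer list |
|---|---|---|
| Neither type | no/weak | no/weak |
| Strong inhibitor only | strong | no/weak |
| Dual moderate inhibitor only | dual moderate, and also moderate | no/weak |
| Rifampin only (a strong inducer in Protocol 5.9.1.3) | no/weak | moderate or strong |
| Inhibitor plus inducer | an exposed group | moderate or strong |
| Ritonavir (noted in Protocol 5.9.1.3 as both inducer and inhibitor) | no placement rule | listed as a strong inducer |

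So each unexposed group admits patients exposed on the other list, and one patient can count twice within the inhibitor list.

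**Step 2: how far the means could move.** The SAP gives no interaction figure to reproduce, so this is an illustration.

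Inputs:
- Inhibitor fold effect Fi = 2.0 for AUC (fluconazole, Protocol 2.1.3).
- Inducer fold effect Fd: not in the documents. 0.50 is assumed, with a range of 0.30 to 0.70.
- q0 and q1, the shares of inhibitor users in the no/weak inducer and the moderate or strong inducer group: not in the documents, assumed.
- r, the share of inducer users in the no/weak inhibitor group: not in the documents, assumed.
- The two effects are assumed to multiply, and the means are arithmetic means of dose-normalised AUC.

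Apparent inducer ratio = Fd × [1 + q1(Fi − 1)] / [1 + q0(Fi − 1)].

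| q0 | q1 | Calculation | Apparent ratio (true 0.50) |
|---|---|---|---|
| 10% | 0 | 0.50 / 1.10 | 0.45 |
| 25% | 0 | 0.50 / 1.25 | 0.40 |
| 40% | 0 | 0.50 / 1.40 | 0.36 |
| 30% | 30% | 0.50 × 1.30 / 1.30 | 0.50 |
| 10% | 50% | 0.50 × 1.50 / 1.10 | 0.68 |

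The first three rows exaggerate the inducer effect, the fourth leaves it unchanged, and the fifth masks part of it.

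**Step 3: the other direction.** Apparent inhibitor ratio = 2.0 / [1 − r(1 − Fd)], assuming no inducer use in the inhibitor group. With r = 10% and Fd = 0.50 this is 2.0 / 0.95 = 2.11. Over r = 2% to 20% and Fd = 0.30 to 0.70 it runs from 2.01 to 2.33.

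**Step 4: parameters that are not dose-normalised.** Protocol 2.1.3 calls for a dose reduction with moderate or strong CYP3A4 or 2C9 inhibitors. If that fully offset the inhibitor effect, Fi would be 1.0 in un-normalised terms and the Step 2 shift would vanish. The trough parameters in SAP 17.1.2 are not dose-normalised. The intensive-day set in SAP 17.2 includes dose-normalised AUC.

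**The case against.** The best defence is that these are two ordinary one-way tables, inhibitor status and inducer status, and one-way tables always overlap across factors. The SAP does the same for age, sex, race and immune status. Naming the dual moderate group separately also suggests that the moderate group was meant for one pathway only. Both readings are reasonable, but neither is written down. Unlike age or sex, the other list here acts directly on the exposure being summarised.

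The adjusted analysis may also sit elsewhere. Protocol 8.11.1 plans a population PK model in which patient-specific factors may be assessed. Protocol 8.2.7 refers sub-categories of the Intensive PK set, including those dependent on concomitant medication, to a modelling plan that is not among the documents. That plan may handle the problem, but it would not change the tables and figures the SAP commits to. The individual listings let a reader see overlap but do not correct the means.

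Other limits stand. The shares of users are unknown. Protocol 2.1.3 discourages strong inducers, so the shift in Step 3 is probably small and the inducer group may not reach three subjects.

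Two stronger readings are tempting. One is that the plan contains formal interaction estimates against a contaminated reference. It contains neither an estimate nor a named reference. The other is that these tables support dose guidance. No section says so: Protocol 5.7 has the guidance available before study start, and Protocol 5.9.1.3, 5.9.1.4 and 5.9.2.1 assess interactions in the individual patient through unscheduled trough samples.

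**Conclusion.** The point holds as a weakness in how descriptive groups are defined. SAP 17.1.1 lets the six groups overlap and gives no rule for patients on several CYP-active drugs. Comparisons of group means can therefore be confounded when use of the other drug type differs between the groups.

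Under the assumed shares of 10% to 40%, a 2.0-fold inhibitor and no inhibitor use among inducer patients, a true ratio of 0.50 would read 0.45 to 0.36. Equal use gives no shift, and heavier inhibitor use among inducer patients moves it the other way. A reader might infer a bias of known direction, but the documents give no shares to support one. The no/weak inducer group is the likelier to be affected, because fluconazole is freely permitted and strong inducers are discouraged.

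The matter is minor. It touches an exploratory objective and a PK endpoint, and leaves the primary efficacy and safety conclusions alone.

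**What to change.** In SAP 17.1.1:

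- Define one comparison group: no moderate or strong CYP2C9/CYP3A4 inhibitor and no moderate or strong CYP3A4 inducer.
- Make the exposed groups mutually exclusive: single moderate inhibitor, dual moderate inhibitor, strong inhibitor, and moderate or strong inducer.
- List patients taking both an inhibitor and an inducer separately, and state where ritonavir goes.
- Base the between-group comparison on dose-normalised intensive-day parameters. Co-medication on that day is known, whereas the trough parameters pool each patient's samples over the whole phase.

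With these groups, q0, q1 and r in the working are all zero for moderate and strong agents, and both illustrative distortions disappear. Weak agents remain in the comparison group.

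The cost is a few lines of SAP text and one derived grouping variable. The comparison group gets smaller: under the illustrative shares it would lose 10% to 40% of the present no/weak inducer group. Some exposed groups may also fall below the three-subject minimum and be listed only.
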